This study is designed to assess the efficacy and economics of two NPWT branded devices of wound healing outcomes. It is also designed to assess the effectiveness of negative pressure and negative pressure with continuous irrigation on multiple parameters of wound healing. It is a single-center, open-label, active controlled, parallel-group trial that aims to determine the efficacy of Quantum with simultaneous irrigation in the treatment of diabetic foot ulcers. Specifically, eligible participants will be randomized to receive either PRO negative press therapy with simultaneous irrigation; or PRO negative pressure therapy without irrigation; or KCI Ultra negative pressure therapy. Primary outcomes will include rates of wound healing, time to closure by secondary intention, and recurrence rate.

Study Objectives and Endpoints

Objective 1

- A) To compare clinical outcomes in Wounds treated with Negative Pressure Wound therapy with and without Simultaneous Irrigation.**

H1: The wound healing outcomes of patients treated with NPWT Pro will be non-inferior to the wound healing outcomes of patients treated with NPWT-KCI Ultra

Primary Endpoint:

- Comparison of reduction in wound volume between wounds treated with NPWT PRO and NPWT-KCI Ultra

Secondary Endpoints:

- Comparison of rate of wound healing in wounds treated with NPWT PRO and NPWT-KCI Ultra.

- Comparison of the following variables between the groups: granulation tissue integrity including hypergranulation state, time to close, flap/graft take, dehiscence, and reoccurrence.

B) To compare clinical outcomes in Wounds treated with NPWT PRO with and without Simultaneous Irrigation.

H1: Patients treated with NPWT with irrigation will have higher proportions of wounds that heal and faster wound healing trajectories compare to patients treated with NPWT without irrigation.

H2: Patients treated with Negative Pressure Wound therapy with Irrigation will have fewer wound complications such as infections, amputations, and foot-related hospital admissions.

Primary Endpoints:

- Primary Endpoint: Comparison of reduction in wound volume between wounds treated with NPWT PRO and NPWT PRO with simultaneous irrigation

Secondary Endpoints:

- Comparison of rate of wound healing in wounds treated with NPWT and NPWT with simultaneous irrigation

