- Comparison of the following variables between the groups: granulation tissue integrity including hypergranulation state, time to close, flap/graft take, dehiscence, and reoccurrence.

Objective 2

To compare bacterial load, quantitative cultures, and clinical infections in wounds treated with NPWT PRO compared to wounds treated with NPWT PRO with simultaneous irrigation.

H1: Bacterial load measured with quantitative polymerase chain reaction (qPCR) will be progressively lower with continuous irrigation.

H2: Patients treated with simultaneous irrigation and NPWT PRO will have fewer infections defined by qPCR and clinical criteria.

Primary Endpoint:

- Comparison of reduction in bacterial load in wounds treated with NPWT and NPWT with simultaneous irrigation.

Secondary Endpoints:

- Comparison of incidence of infection in wounds treated with NPWT and NPWT with simultaneous irrigation.
- Infection-induced necrosis
- Infection reoccurrence post-closure

Objective 3

Assess changes in molecular markers associated with wound healing and regeneration of healthy tissue.

H1: NPWT PRO with simultaneous Irrigation will improve the levels of growth factors, cytokines, and other molecular markers over NPWT PRO alone.

H2: Negative pressure wound therapy will drive molecular changes in growth factors and other cytokines associated with regeneration of healthy tissue.

Primary Endpoint:

- To compare changes in genes and other molecular markers associated with wound healing between wounds treated with NPWT and NPWT with simultaneous irrigation.

Secondary Endpoint:

- To compare the addition of simultaneous irrigation on gene expression and expression of molecular markers from baseline.

Objective 4

Quality of Life and Patient Satisfaction Analyses

H1: Patients treated with the NPWT PRO device will show greater patient satisfaction with treatment than those treated with KCI Ultra NPWT therapy.

Primary Endpoints:

- To compare Quality of Life and Patient Satisfaction between patients treated with NPWT PRO versus patients treated with KCI Ultra NPWT therapy.
- To compare Quality of Life and Patient Satisfaction between patients with wounds treated with NPWT PRO versus NPWT PRO + SI.
- Evaluate functional status, using the Short Form 36 (SF36). These will be administered at baseline and at the last study visit.

Subjects and Recruitment

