The inpatient stay and post-operative visits are covered under a 90-day global payment which is inclusive of all procedures, devices, testing and ancillaries associated with the surgical procedure, including NPWT. Subjects’ insurance will not be charged any additional amount for the NPWT devices used in the study. The KCI devices are standard at Parkland; Cardinal is providing their devices. But again, in neither situation would a subject or their third party pay or be charged anything additional.

Survival Analyses Models

The primary analytical method presented in this report is based on a time-to-event strategy using Kaplan-Meier estimates, followed by a log-rank test. This statistical procedure provides a comparison of the distribution of events between the 2 treatment groups. In addition to the event rates calculated for the post-baseline time points, the median time to 100% closure, 75% closure, and 76-100% wound bed granulation will also be calculated. This same methodology will also be used to compare the overall duration of treatment, and within the individual patient subsets defined by their outcome status.

A Cox proportional hazard model will be used to relate time to specific events to various risk factors. The main modeling strategies will look at the time to adverse events with time being measured from the time of surgery or the time of NPWT application until either an adverse event occurs, the patient is considered healed, or the end of the study. Cox proportional hazard model allows the independent variables to be continuous covariates or categorical or binary factors. The type of NPWT treatment will be the main independent variable. We will use multivariate proportional hazard regression analysis methods to investigate what factors are significant for non-healing patients or patients that have complications. Similar to the logistic regression, maximum likelihood estimates of model parameters along with tail probabilities (p-values) and confidence intervals for parameters

will be derived based on asymptotic inferences. For the proportional hazard model the ratio of the hazards for two subjects one with and one without diabetes, given that the subjects have the same values for other parameters can be estimated from the model coefficients. Repeated measures ANOVA and ANOVA will be used to evaluate changes in quantitative cultures and laser Doppler measurements over time and between treatment groups.

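### The plan names conflicting primary endpoints, sizes the trial on another endpoint, and fixes no testing order, analysis alpha or deciding pair of arms

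*Combined protocol and SAP*

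**What the plan says.** **Design paragraph (Study Groups and Design).** "Primary outcomes will include rates of wound healing, time to closure by secondary intention, and recurrence rate". No pair of arms is attached to these three outcomes.

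**Objectives (Study Objectives and Endpoints).** Each objective carries its own primary label:
- 1A, device question, framed as non-inferiority: "Comparison of reduction in wound volume between wounds treated with NPWT PRO and NPWT-KCI Ultra".
- 1B, irrigation question: "Comparison of reduction in wound volume between wounds treated with NPWT PRO and NPWT PRO with simultaneous irrigation".
- Objective 2: "Comparison of reduction in bacterial load in wounds treated with NPWT and NPWT with simultaneous irrigation".
- Objective 3: "To compare changes in genes and other molecular markers associated with wound healing between wounds treated with NPWT and NPWT with simultaneous irrigation".
- Objective 4: "To compare Quality of Life and Patient Satisfaction between patients with wounds treated with NPWT PRO versus NPWT PRO + SI". A parallel PRO versus KCI comparison and an SF-36 evaluation with no named contrast are also listed as primary.

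Under 1A and 1B, rate of healing, time to close and reoccurrence are secondary endpoints.

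**Biostatistics.** Sample Size Justification and Equations use the proportion of wounds surgically closed, 60% versus 90%, and tabulate alpha at 5% and 10% without choosing between them. Survival Analyses Models names Kaplan-Meier estimates with a log-rank test as the primary method and adds: "This statistical procedure provides a comparison of the distribution of events between the 2 treatment groups". Randomization is 1:1:1 to three arms, with 90 patients in total. The section gives no testing order, alpha split or exploratory label.

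**The concern.** A reader cannot say in advance which result would make the trial positive for irrigation. The objectives point to volume, load, markers and patient-reported outcomes. The design paragraph points to healing rate, closure time and recurrence. The sizing points to proportion closed, and the analysis section to a time-to-event comparison. Three outcomes are both primary and secondary. This is a contradiction between stated rules, and not only missing detail.

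The candidates can also disagree. In the protocol's own porcine study, adding irrigation lowered bioburden beyond NPWT alone, while wound healing did not differ from NPWT alone. If that pattern recurred here, one labelled primary (load) would be positive and another (volume) negative in the same patients, and nothing in the plan says which governs. Without a rule, the choice can be made after the data are seen, and the chance of some false primary finding rises above the nominal level.

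**Working it through.** **1. Reproduce the plan's own figure.** With P1 = 0.60, P2 = 0.90, mean P = 0.75 and power 0.80, the plan's formula gives:
- alpha 0.10: (1.645 × 0.6124 + 0.8416 × 0.5745)² / 0.30² = 24.7, so 25 per arm (plan: 25).
- alpha 0.05: (1.960 × 0.6124 + 0.8416 × 0.5745)² / 0.30² = 31.5, so 32 after rounding up (plan: about 31).

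The sizing therefore stands as a two-group comparison of closure proportions. It concerns none of the endpoints that the objectives label primary.

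**2. Count the irrigation primaries.**
- Volume, load, markers, and quality of life with satisfaction taken together: 4.
- Quality of life and satisfaction counted separately: 5.
- Adding the three design-paragraph outcomes, if they are read as irrigation tests: 7 or 8.

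Objective 1A is a device question and is left out. Objective 3 counts as one test although its array covers 84 genes. The SF-36 item is not counted separately.

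**3. Chance of at least one false positive, with no true effect.**
- Independent tests: 1 − (1 − α)^k. At α = 0.05: k = 4 gives 1 − 0.95⁴ = 0.185; k = 8 gives 1 − 0.95⁸ = 0.337.
- Common pairwise correlation ρ, two-sided, critical value c = 1.96: 1 − ∫ [Φ((c − √ρ·x)/√(1−ρ)) − Φ((−c − √ρ·x)/√(1−ρ))]^k φ(x) dx, integrated numerically.
- Errors favouring irrigation only: the same integral without the lower-tail term, at 2.5% per test.

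| Tests | Two-sided 5%: ρ = 0 | ρ = 0.5 | ρ = 0.8 | Favourable 2.5%: ρ = 0 | ρ = 0.5 | ρ = 0.8 |
|---|---|---|---|---|---|---|
| 4 | 18.5% | 15.6% | 11.4% | 9.6% | 7.8% | 5.7% |
| 5 | 22.6% | 18.3% | 12.7% | 11.9% | 9.1% | 6.4% |
| 7 | 30.2% | 23.0% | 14.9% | 16.2% | 11.5% | 7.4% |
| 8 | 33.7% | 25.0% | 15.7% | 18.3% | 12.5% | 7.9% |

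The smallest entries, 11.4% and 5.7%, are each about 2.3 times their nominal level (11.4/5 and 5.7/2.5).

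**4. The plan's other alpha.** At two-sided 10% per test and ρ = 0.5, 4 tests give 28.8% and 8 tests give 43.5%.

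The correlations and the per-test alpha are assumptions, because the documents state neither.

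**The case against.** **Separate objectives, separate claims.** Load, gene expression and satisfaction answer different questions, and the plan nowhere says that success on any one makes the trial positive. This has force, and it is why the device question is kept apart here. A reader might infer that the sponsor intends to claim success on whichever endpoint is significant. The documents do not say that; they leave the matter open.

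**The count.** A reader might infer eight distinct chances for irrigation. The documents do not establish eight: the three design-paragraph outcomes name no contrast and recur as secondaries, and Objective 4's only stated hypothesis is PRO versus KCI on satisfaction. Four is as defensible as eight, so the range is shown. Adding the PRO versus KCI comparisons of Objective 4 would be wrong, since they say nothing about irrigation.

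**The size.** A reader might take 18-25% as the established error rate. It applies only to 5 to 8 tests at correlation 0.5 and two-sided 5%, and half of those errors would show irrigation as worse. The favourable-direction figures are about half as large, though still well above 2.5%.

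**Pilot purpose.** Sample Size Justification says that one purpose is to obtain data to power a larger multicenter study. That lowers the stakes. It is only one of the purposes, however: every objective states hypotheses, Biostatistics describes a non-inferiority conclusion, and the Innovation section expects the results to help clinicians develop treatment protocols.

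**Conclusion.** The concern stands as a contradiction over what is primary. Objectives, design paragraph, sizing and primary method do not agree on the deciding endpoint, and the deciding pair of arms and the analysis alpha are not fixed.

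The numerical consequence is conditional. If 4 to 8 irrigation primaries were each tested at two-sided 5%, the chance of at least one false positive would lie between 11% and 34% for correlations from 0.8 to 0. For errors favouring irrigation it would be about 6-18%, against 2.5% for one test. No single figure in those ranges can be drawn from the documents, but the error is more than twice nominal at every point examined. The correction should be made before analysis; the data-gathering purpose moderates its weight.

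**What to change.** Before analysis, state one deciding endpoint, contrast and alpha for each question:
- **Irrigation:** PRO with irrigation versus PRO, Objective 1B wound volume reduction, two-sided 0.05.
- **Device:** PRO versus KCI non-inferiority, Objective 1A wound volume reduction, one-sided 0.025, reported as its own question.

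Name the analysis for volume; Biostatistics currently ties no superiority test to it. State that the closure-based sample size and the log-rank test do not apply to volume. Alternatively, choose closure as the single deciding endpoint, so that sizing, method and endpoint agree.

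Name the pair of arms in the log-rank sentence. Relabel the other primary endpoints as secondary or exploratory, reported with estimates and 95% intervals. Bacterial load may be kept as a key secondary, tested only if the irrigation contrast is significant; this is optional. Bring the design-paragraph sentence on primary outcomes into line.

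The cost is protocol and SAP text, including a volume analysis that has yet to be written; no patients, visits or data are added. The sponsor gives up the option of presenting a significant result on load, markers, quality of life or satisfaction as a primary success. If volume is kept, the sponsor must also acknowledge that the stated sample size was not derived for it.

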If evaluation of the clinical indicators suggest the presence of significant bacterial infection of the wound, swab culture, utilizing swab technique [126] will be performed to confirm or reject the presence of significant bacterial infection severe enough to warrant the subject terminated from the study. The swab culture will be performed using a laboratory-provided swab that is pressed down over a 1 cm² area of the wound that is then delivered to the lab for analysis to determine Colony-Forming Units (CFUs) per gram of viable wound tissue and beta-hemolytic Streptococcus per gram of tissue. The findings of a positive or negative swab culture utilizing Levine's technique will be interpreted according to the following criteria:

- Positive culture indicating presence of bacterial infection: $\geq 1,000,000$ Colony-Forming Units (CFUs) per gram of viable wound tissue OR containing beta-hemolytic Streptococcus per gram of tissue at any level.
- Negative culture indicating absence of bacterial infection: $< 1,000,000$ Colony-Forming Units (CFUs) per gram of viable wound tissue OR no beta-hemolytic Streptococcus per gram of tissue at any level.

Tissue specimens will be obtained from the chronic wounds using 1) wound exudate, 2) broad Z-technique, and 3) Levine technique [126]. Acquisition of swab specimens was followed with a wound tissue biopsy. The diagnostic validity of each technique was determined by associating the quantitative culture findings of each swab specimen with the culture findings of concurrent tissue specimen (gold standard). Levine's technique performed best of the three swab techniques in terms of all four validity parameters: sensitivity was, specificity, positive predictive value, and accuracy.

Bio-burden

Bio-burden will be assessed using qPCR to quantify bacterial load from serial tissue specimens. Specific organisms that will be quantified using qPCR are listed in the table below. Bone, soft tissue will be sent to Research and Testing Laboratory (Lubbock, TX) for analysis.

Specific organisms (and two resistance factors) to be quantified using qPCR.			
E. faecalis	E. faecium	S. epidermidis	M. morgani
K. pneumonia	S. aureus	C. striatum	S. haemolyticus
S. agalactiae	S. marcescens	F. magna	S. mutans
S. pyogenes	H. influenzae	P. mirabilis	Vancomycin res.
C. albicans	M. catarrhalis	C. parapsilosis	Methicillin res.
P. aeruginosa	S. pneumoniae	A. baumannii	Total Bioburden

Osteomyelitis

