 - It is anticipated that most wounds will be determined ready for surgical wound closure by 4 weeks of therapy administration; however this may occur as early as after 2 weeks or subjects may be followed up to the full 12 weeks, and closure may occur anywhere inbetween (to be determined by investigator). It is also possible for some subjects that the wound may not be ready for closure even after 12 weeks. These subjects will be discharged from the study at that time and continue appropriate care for their wound with their physician.
 - The surgical wound closure procedure is performed in the operating room, using the most applicable of the following common mechanisms for closure, as is optimal for the individual subject and wound: delayed primary closure, rotational flap to close the wound, split thickness skin graft.
- Post Wound Closure Evaluation Phase
 - Following surgical closure of the wound, the subject will enter the post wound closure evaluation phase. This phase will last up to week 12 following study enrollment and therapy administration start, such that the duration of the post wound closure evaluation phase will vary for each subject according to the time point at which their wound was deemed ready for surgical closure. For example, a subject whose wound is surgically closed after week 4 of the therapy administration phase will enter a post wound closure evaluation phase that spans from week 5 through week 12, at which time the subject will exit the study. A subject whose wound does not close sufficiently for surgical repair by week 12 will exit the study at that time without entering the post wound closure evaluation phase.
 - The post wound closure evaluation phase will comprise weekly or standard of care evaluations in the outpatient clinic setting. If the wound remains closed with no sign of re-opening or infection, no further efficacy or safety evaluations will be taken at that visit. At post therapy

administration phase completion (as applicable to the individual subject), a standard of care blood draw will again be taken as at the baseline evaluation to assess lab markers.

- If at any of the post wound closure evaluation visits, the wound is found to have re-opened and/or shows signs of infection, the following will occur at the discretion of the physician:
 - Measurements of dehiscence will be taken
 - Surgical debridement of the wound will be done
 - NPWT only will be reapplied per standard of care

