 - The subject will re-enter the therapy administration phase including the weekly or standard of care efficacy and safety evaluation test site visits and procedures.

Home Health Visits

The study therapy will only be given while the subject is in the hospital. If the subject's wound is not ready for closure during the hospital stay, the subject will continue NPWT at home. NPWT at home will be without irrigation. If the subject continues to receive NPWT after hospital discharge, the subject will be seen twice weekly by a home health nurse for dressing changes. The home health nurse will collect sitting blood pressure and pulse rate. Amount, type and character of wound drainage will be documented, as well as any adverse events and changes to concomitant medications. Offloading will be reapplied after dressing changes. At the same time, subject will continue to be followed by the study doctor during regular post-operative visits at outpatient clinic. If the wound closes, End of study visit will be performed and she/he will see the study doctor at outpatient clinic to have the closed wound checked.

Safety and Efficacy Evaluation

During the study therapy administration and evaluation phase, the subject will attend once weekly or standard of care test site visits, commencing at the end of Week 1 of therapy administration and ending at the weekly or standard of care visit where the wound is determined ready for surgical closure and the therapy administration process is complete.

- Weekly or standard of care Efficacy Evaluations
 - Digital Photography of the Study Wound
 - Wound Measurement (using a ruler and the eKare Insight System)
 - Granulation Tissue Estimation
 - Additionally, at the final week of efficacy evaluation test site evaluation, Subject Satisfaction with Study Procedure Outcome Evaluation will be performed.
- Weekly or standard of care Safety Evaluations
 - Safety Measures
 - Debridement Indication
 - Degree of Pain Rating
 - Infection Evaluation: encompassing swab culture and osteomyelitis assessment, if indicated.
- Inpatient Tissue Samples
 - Tissue samples will be taken and kept, for research, at inpatient study visits prior to wound closure for the following analyses.
 - For bacterial analyses
 - For gene expression analyses
 - After wound closure, no samples will be taken unless wound reoccurrence occurs.
 - Samples will be approximately 0.25-0.5 cm³ in size

- Bio-burden: qPCR evaluation
- Other Activities

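### The swab-culture rule labels a specimen that meets exactly one infection criterion as both positive and negative

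*Combined protocol and SAP*

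**What the plan says.** The Swab Culture subsection of Infection Evaluation sets out when a swab is taken, what is measured and how the result is read.

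- **Who is swabbed.** Only some subjects: "If evaluation of the clinical indicators suggest the presence of significant bacterial infection of the wound". The indicators are listed just above, under Clinical Indicators. The weekly or standard-of-care safety evaluations carry the same restriction: "Infection Evaluation: encompassing swab culture and osteomyelitis assessment, if indicated".
- **What it is for.** The culture "will be performed to confirm or reject the presence of significant bacterial infection severe enough to warrant the subject terminated from the study".
- **What is measured.** The laboratory reports both a colony count per gram and beta-hemolytic Streptococcus on each swab.
- **How it is read.** Findings from Levine's "technique will be interpreted according to the following criteria". A culture is positive, meaning infection is present, at 1,000,000 or more CFU "per gram of viable wound tissue OR containing beta-hemolytic Streptococcus per gram of tissue at any level". The other line is headed "Negative culture indicating absence of bacterial infection" and applies below 1,000,000 "Colony-Forming Units (CFUs) per gram of viable wound tissue OR no beta-hemolytic Streptococcus per gram of tissue at any level".

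Both lines use OR. Neither is given precedence, here or elsewhere in the document.

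**The concern.** Two labels that mean presence and absence of infection should divide the possible results between them with no overlap. The negation of a rule that asks for either of two findings is that neither finding is there, so the negative line has to require both a low count and no Streptococcus. As worded, it is satisfied when just one of the two findings is missing.

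The overlap falls on the results where the rule is most needed. The positive line counts Streptococcus at any level, evidently so that a low count does not excuse it. The negative line, read literally, does excuse it: a streptococcal swab with a low count qualifies as showing no infection. So does a heavily colonised wound without Streptococcus. Both results would come from wounds that already looked infected, and the test is meant to settle whether the infection is serious enough to end participation. A test meant to confirm or reject cannot do both on one specimen. The trial is also open-label (Study Groups and Design), so without a written tie-break the label may be settled by staff who know the treatment arm.

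**Working it through.** The protocol states no figure on this point, so there is none to reproduce. The check lists every possible result and applies the two lines to each.

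**Inputs** (all from Swab Culture)

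- A: count of at least 1,000,000 CFU per gram.
- B: beta-hemolytic Streptococcus present at any level.
- Both are reported on each swab, so there are 2 × 2 = 4 patterns.

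**Rules**

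- Positive, as written: A or B.
- Negative, as written: (not A) or (not B).
- True complement of the positive rule: not (A or B) = (not A) and (not B).

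**Result**

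| Count | Streptococcus | Positive line | Negative line as written | Negative line with AND |
|---|---|---|---|---|
| ≥ 1,000,000 | present | met | not met | not met |
| ≥ 1,000,000 | absent | met | **met** | not met |
| < 1,000,000 | present | met | **met** | not met |
| < 1,000,000 | absent | not met | met | met |

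**Counts as written.** Three patterns meet the positive line, three meet the negative line, two meet both and none meets neither (3 + 3 − 2 = 4). Of the three positive patterns, two are also negative. Of the two patterns with Streptococcus, one is also negative; the same holds for the two with a high count.

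**Counts with AND.** Three patterns are positive, one is negative, none is both and none is neither (3 + 1 = 4). None of the three positive patterns is also negative.

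The two bold rows are exactly those in which one criterion is met and the other is not.

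**The case against.** The strongest reply is that this is a drafting slip whose intended meaning is hard to miss. The positive line is explicit and sufficient, and a line headed as negative is naturally read as neither of the above. To call a streptococcal swab negative, staff would have to ignore the line directly above it. That is probably how many readers will take it. But it requires the same capitalised OR to mean either in one line and both in the next, and the document does not say so.

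A second reply is that little depends on the label, and much of this stands:

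- No planned analysis uses the positive or negative swab result. Objective 2 (H2) defines infection by qPCR and clinical criteria, and the Biostatistics section analyses quantitative cultures and qPCR data without this dichotomy. Any effect on the infection endpoint is at most indirect.
- Care does not wait on the label. Clinical indicators are recorded separately and come before the swab. Infection found on physical examination is an indication for debridement under Standard of Care Regimen. In the Post Wound Closure Evaluation Phase, if the wound re-opens or "shows signs of infection, the following will occur at the discretion of the physician", and what follows includes debridement, reapplied NPWT and re-entry to the therapy phase.
- Nothing in the available text makes withdrawal automatic on a positive culture. The adverse-event section points to a subject-withdrawal section that is not in the public text, so what it may say is unknown.

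These points limit the weight of the finding. They do not remove the contradiction, because clinical discretion does not make a written criterion consistent or ensure that it is recorded the same way each time.

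**Conclusion.** The concern holds. As written, the swab rule gives both labels to 2 of the 4 result patterns, including 2 of the 3 that the positive line treats as infected. This follows from the wording alone; the only assumption is that OR means the same in both lines.

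The size must not be read as a rate. The document gives no frequencies for the four patterns, so the number of subjects affected cannot be estimated, and it can include only those swabbed on clinical suspicion, not all 90. The conclusion concerns the label and the confirm-or-reject decision that the label is meant to support. No harm to care is shown. The error should be corrected because the rule is operative and bears on whether a subject stays in the study.

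**What to change.** In the negative line of Swab Culture, change OR to AND, so that a culture is negative only when the count is below 1,000,000 CFU per gram of viable wound tissue AND no beta-hemolytic Streptococcus is found. Leave the positive line as it is. The two lines then cover every result once, and no separate tie-break is needed.

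The cost is one word in the protocol. Sample size, visits, laboratory work and the data collected do not change.
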